#### **Safety Analysis**

The incidence of any adverse events (AEs) will be determined. Gastrointestinal and systemic AEs will be assessed postvaccination using participant/parent/guardian interview (including memory aids), targeted physical examinations, vital signs and clinical laboratory tests and reactogenicity assessments to be completed following each vaccination. The solicited AEs of nausea (Part A only), abdominal pain/stomach ache (Parts A and B only), fever, vomiting and diarrhea will be evaluated daily by the TSS for 7 days post vaccination. Unsolicited AEs will be assessed through Day 42 and serious adverse events (SAEs) will be assessed over the entire duration of the study. Proportions of subjects with events, overall, by grade and relationship with vaccination will be analyzed for each of the vaccine arms in comparison to the placebo arm. For the analysis of the solicited adverse events, the statistical comparisons using Fisher's exact test will be performed using two-sided 5% Type I error rate without an adjustment for multiple comparisons. The primary purpose of statistical comparisons are to screen potential AEs that need further clinical evaluation. Therefore they are not considered formal statistical hypothesis testing and it is acknowledged that there will be an inflated Type I error rate (i.e. inflated false statistical significances) due to performing multiple testing without an adjustment.

Safety will be assessed by analyses of the following primary endpoints (events), where the unit of analysis in each case will be the proportion of participants with at least one event:

- Solicited gastrointestinal reactions
- Solicited systemic reactions
- Unsolicited adverse events
- Adverse events where there is a reasonable possibility that the study product caused the event, i.e., are suspected adverse reactions
- Serious adverse events

#### Immunogenicity Analysis

For all immunological analyses, the response rate and magnitude of antigen-specific responses will be analyzed after each immunization as specimen availability allows; as well as the cumulative response rate after two immunizations (i.e. response after either immunization). Response rates to the five primary antigens in the ETVAX vaccine (LTB, CFA/I, CS3, CS5, and CS6) will be further evaluated to address co-secondary immunogenicity hypothesis by analyzing the response rates to at least two of the five different antigens by ALS IgA and fecal SIgA and to at least one of the five different antigens by plasma IgA. In addition, other analyses summarizing response rates to multiple antigens may also be performed. These multiple antigen response rate analyses will be based on the results from antigen-specific responses, including different age cohorts. For example, only antigens with statistically significant and/or clinically meaningful vaccine induced responses may be included in the analysis of multiple common antigen analyses.

For descriptive analysis of the magnitude of responses, levels of antibodies against CFA/I, CS3, CS5, CS6 and LTB in ALS and fecal extracts as well as plasma will be determined for each individual during screening and in all post vaccination samples. The geometric mean (GM) of antibody levels and the GM of fold-rises (post vaccination / pre-vaccination) will be determined for each study group and comparisons made between pre- and post-vaccination levels. The response rate for ALS IgA, fecal SIgA, serum IgA and serum IgG will be determined as the proportion of participants having a  $\geq$ 2-fold increase in antigen-specific antibody levels between pre- and post-vaccination samples. Additionally, other fold increases (e.g. 3-fold and 4-fold) will be explored. If insufficient amounts of pre-immune ALS specimens are obtained from young children and infants, to allow direct comparison between pre- and post immunization specimens, antibody levels in post vaccination specimens will be compared with the geometric mean ALS antibody level against corresponding antigen in the same age group.

For each endpoint, two-sided 95% confidence Interval (CI) will be constructed using the Clopper-Pearson method for the response rate or log-normal distribution for GMT/GMFR. Primary statistical comparison of immune response frequencies and magnitudes in vaccine and placebo recipients will be carried out using standard parametric and non-parametric methods whichever is applicable (i.e. Fisher's exact test, Chi-square test, t-test, and Mann-Whitney U test for two group comparisons; and Chi square test, generalized linear model, and Friedman's test). For GMT and GMFR antigen specific endpoints, the log values will be used for the analyses. The log mean and the corresponding CI limits will then be exponentiated to obtain the GMT/GMFR and the corresponding CI. Statistical comparisons will be made between ETVAX dose levels and the dmLT levels, as well as comparison to the placebo group.

Due to the exploratory nature of all statistical comparisons for immunogenicity endpoints, all testing and estimations will be carried out using a 2-sided 5% Type I error rate without an adjustment for multiple comparisons. However within each

immunogenicity endpoint in the infants, Holm's correction for multiple testing will be applied to control the multiple comparisons associated with multiple treatment groups.

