# Overview and general design

This study is a randomized, double-blind, dose-escalation, descending age clinical trial to assess the safety and immunogenicity of the inactivated whole cell ETVAX vaccine administered alone and with dmLT adjuvant as compared to a placebo (bicarbonate buffer). The primary objectives are to evaluate the safety and tolerability of the inactivated whole cell ETVAX vaccine with and without dmLT adjuvant in adults, toddlers, young children and infants.

The secondary objectives are:

- 1. To assess vaccine induced IgA antibody responses in lymphocyte secretions (ALS) against LTBD, CFA/I, CS3, CS6 and CS5 in descending age-groups in Bangladesh
- 2. To evaluate vaccine induced fecal secretory IgA (SIgA) antibody responses against CFA/I, CS3, CS5, CS6, O78 LPS and LTB in applicable age-groups in Bangladesh
- 3. To assess vaccine induced plasma IgA antibody responses against LTB, O78 LPS, CFA/I, CS3, CS6 and CS5 and IgG antibody responses against LTB and O78 LPS
- 4. To evaluate vaccine induced ALS IgA responses against O78 LPS (if sample volumes allow)
- 5. To assess adjuvant effect of dmLT on vaccine immune responses compared to responses when giving vaccine alone in descending age-groups in Bangladesh.

The secondary hypothesis of immunogenicity will be fulfilled if at least 50% or more of fully immunized young children and infants show significantly higher mucosal immune responses to at least two out of the five vaccine antigens tested (LTB, CFA/I, CS3, CS5, and CS6) by ALS IgA and or fecal SIgA/total SIgA assays compared to placebos.

A detailed statistical analysis plan for preparation of the final study report will be created and made final prior to database lock and unblinding for each age group.

Medical history and AEs will be coded using MedDRA® dictionary Version 16.1 or higher. The frequencies and percentages of participants with AEs will be summarized according to the coded terms of system, organ, class (SOC) and preferred term. Participant-wise data listings will be provided.

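### Optional multi-antigen response analyses may be restricted to antigens that already looked positive in the same participants, which biases the vaccine–placebo contrast in favour of vaccine

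*Protocol*

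**What the plan says.** The protocol's Immunogenicity Analysis section deals with multi-antigen responses in two steps.

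- **Fixed analysis.** The secondary immunogenicity hypothesis is addressed by "analyzing the response rates to at least two of the five different antigens by ALS IgA and fecal SIgA", with a one-of-five version for plasma IgA. The section Overview and general design names the same set: "at least two out of the five vaccine antigens tested (LTB, CFA/I, CS3, CS5, and CS6").
- **Optional analyses.** The section continues: "In addition, other analyses summarizing response rates to multiple antigens may also be performed". On their content it says: "These multiple antigen response rate analyses will be based on the results from antigen-specific responses, including different age cohorts". The example given is that "only antigens with statistically significant and/or clinically meaningful vaccine induced responses may be included in the analysis of multiple common antigen analyses".

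The protocol gives no threshold for a clinically meaningful response. It does not say whether significance means against placebo or against baseline. It does not require that the results used to choose antigens come from participants other than those then compared.

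On error control, the same section states that "all testing and estimations will be carried out using a 2-sided 5% Type I error rate without an adjustment for multiple comparisons". The reason it gives is that the immunogenicity comparisons are regarded as exploratory throughout. In infants, "Holm's correction for multiple testing will be applied to control the multiple comparisons associated with multiple treatment groups". That correction runs across treatment groups within an endpoint. It does not cover selection among antigens.

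**The concern.** An antigen can enter the composite because it already separated vaccine from placebo, and the composite is then compared between those same arms. The second comparison partly repeats the first. Antigens that were high by chance in the vaccine arm are kept and the others dropped, so the estimated difference is too large and its confidence interval is centred in the wrong place.

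At stake is how far a multi-antigen result can be trusted. Breadth of response is part of the third secondary hypothesis. The Interim Analysis section also allows an unblinded analysis of each Part after Day 42 to support decisions outside the trial, such as preparing another study. A composite of selected antigens could be read there as evidence of breadth.

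**Working it through.** The protocol gives no power, rate or error figure for these analyses, so there is nothing to reproduce. The check is a calculation and simulation under no vaccine effect.

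**Inputs from the protocol.** Part D has 30 vaccinees and 10 placebo infants per cohort, in five cohorts. There are five antigens. Fisher's exact test is among the listed tests, at two-sided 5%, unadjusted.

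**Assumptions.** Placebo infants are pooled over cohorts (5 × 10 = 50). Null response rates are 10–30%, equal in both arms. The five responses have latent correlation 0 or 0.3. An antigen is selected if it is significant against placebo in favour of vaccine. Where a threshold stands in for clinical meaning, it is an observed difference of at least 10 points.

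**Step 1: chance selection.** For one antigen with null rate p, the probability of a falsely favourable result is the sum of Bin(a; 30, p) × Bin(b; 50, p) over all tables with a/30 > b/50 and Fisher p < 0.05. This gives 1.92%, 1.80% and 1.88% for p = 10%, 20% and 30%. For at least one of five independent antigens:

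- p = 10%: 1 − (1 − 0.0192)^5 = 9.2%
- p = 20%: 1 − (1 − 0.0180)^5 = 8.7%
- p = 30%: 1 − (1 − 0.0188)^5 = 9.0%

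**Step 2: testing the selected composite.** When one antigen is selected, the composite of at least one selected antigen is that antigen, so its test is significant by construction. Two or more are selected in under 1% of null trials. The composite is therefore significant in 99–100% of trials with any selection, and the overall false-positive rate is close to the step 1 figure.

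**Step 3: simulated null results, 30 vs 50, in favour of vaccine.**

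| Rule | Falsely significant |
|---|---|
| Fixed, at least 2 of 5 | about 2% (runs 1.4–2.3%) |
| At least 1 significance-selected antigen | about 8–9% (runs 7.6–9.5%) |
| At least 2 significance-selected antigens | below 1% |
| At least 2 antigens kept at the 10-point threshold | 0.4–6.5% |

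A fixed at-least-1-of-5 rule also gives about 1.9% (correlation 0.3), so the rise in the second row comes from selection and not from the lower count. The mean spurious difference for that row, when any antigen is selected, is 18–27 points.

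**Step 4: independent selection.** If antigens are chosen in one data set and compared in another (null rate 20%, correlation 0.3), the bias is 0.1–0.4 points. False significance is 2.2% for at least one selected antigen and 3.5% for at least two, the latter from few replicates.

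**Step 5: when the vaccine works.** With true rates of 40% vs 20% for two or for all five antigens, same-data selection overstates the composite difference by 9–11 points. At 60% vs 10% for all five, every antigen is in effect kept and the bias is about 0.

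**Sensitivity to group size.** At 15 vs 40 (one Part C vaccine group against four pooled placebo groups) and a null rate of 30%, the at-least-one rule gives about 9.3%. At 15 vs 10 without pooling, Fisher's test is so conservative that the rate is 0.03–4.7% over null rates of 10–30%. When an antigen is selected there, the spurious difference is 45–49 points.

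**The case against.** The strongest reply is that the sentence governs little. It is an example, worded as permission, within additional analyses described as summaries. All immunogenicity comparisons are declared exploratory, and this is a Phase I/II trial with safety as its primary objective. That stands and limits the consequence. It does not remove the bias in a point estimate that would still be reported.

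A reader might infer more than the document supports:

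- **That the secondary hypothesis is tested on selected antigens.** It is not. The at-least-two-of-five composite is fixed and is analysed whatever the optional analyses do.
- **That the 50% target in the first secondary hypothesis becomes easier to meet.** It does not. That target is a rate within the vaccinated group, and dropping antigens can only leave unchanged or lower a participant's count of positive antigens. The bias lies in the contrast with placebo.
- **That every version of the selected composite has inflated error.** Requiring two significance-selected antigens gives fewer false positives than the fixed rule, because two are rarely selected by chance. With the 10-point threshold the result depends on the null rate and correlation.
- **That use of other age cohorts is itself the fault.** Choosing antigens for a younger Part from an older Part's results is close to unbiased (step 4). The difficulty is that the text includes other cohorts without limiting the selection to them.
- **That the figures carry over to adjuvanted versus unadjuvanted vaccine.** That comparison was not simulated.

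One could also leave the matter to the statistical analysis plan, which is to be final before unblinding of each age group. But the protocol here states a rule, and a plan that follows it faithfully would carry the problem forward.

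**Conclusion.** The point holds within a limited scope. The protocol expressly permits optional multi-antigen analyses to be restricted to antigens chosen on the trial's own results, and neither separate data nor any correction is required. Where the same participants serve both purposes, the vaccine–placebo contrast is biased towards vaccine.

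The clearest case is response to at least one significance-selected antigen: about 8–9% false positives against about 2%, and a spurious 18–27 points when any antigen is selected. This rests on 30 vs 50 with pooled placebo, null rates of 10–30%, correlation 0–0.3, and reading significance as a comparison with placebo. Rules requiring two kept antigens show smaller error rates or no inflation, and very large true effects leave almost no bias. The analyses tied to the secondary hypothesis are unaffected. The sentence is worth correcting because it builds in an avoidable bias, not because it endangers a main conclusion.

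**What to change.** Replace the example sentence with a rule on these lines:

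- Every multi-antigen response rate uses the fixed set LTB, CFA/I, CS3, CS5 and CS6, or a subset that is named before unblinding of that Part or chosen from independent data (OEV-121 or an earlier age Part).
- Any subset chosen on the results of the same participants is labelled post hoc, reported beside the five-antigen composite, and given no p-value.

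The cost is a wording change in the protocol, carried into the statistical analysis plan. No participants, samples, visits or assays change, and the fixed analysis for the secondary hypothesis stays as it is.

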### **Secondary Hypotheses:**

Immunogenicity

- 1. The vaccine regimens under testing will elicit mucosal immune responses to at least two of the antigens in 50% or more participants in at least one of the dosing regimens in young children or infants
- 2. The responses induced by the vaccine regimens tested will be higher and/or more frequent than the responses in the placebo group.
- 3. In the event that dmLT is used, adjuvanted vaccine will induce stronger (increased magnitude and/or breadth of response) intestinal and/or intestine-derived and/or plasma anti-LTB and anti-CF/CS antibody responses than the ETVAX alone in young children and infants.

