#### Per Protocol Populations

The per protocol populations will be specified per sample and antigen type. All participants in the FA population who receive both doses of the same study vaccine and have post second dose (all sample types) and pre-vaccination (stool and plasma) immunogenicity measurement(s), with no major protocol or laboratory test SOP violations that are determined to potentially interfere with the immunogenicity assessment of the study vaccine, will be included in the per protocol populations. These populations will serve as the primary analysis populations for the immunogenicity objectives.

The specific criteria for exclusion of subjects from the Per Protocol Populations will be established before breaking the blind and will be based on the blinded review of protocol and laboratory test SOP violations

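### The fallback ALS comparison with an age-group geometric mean replaces a personal baseline with a group centre, so its response rate is distorted and cannot be read against the 50% hypothesis

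*Protocol*

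**What the plan says.** The standard rule, in Immunogenicity Analysis, scores a participant as a responder for at least a "2-fold increase in antigen-specific antibody levels between pre- and post-vaccination samples". Response after either dose counts towards a cumulative rate.

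The fallback follows directly: "If insufficient amounts of pre-immune ALS specimens are obtained from young children and infants", to the point that pre and post specimens cannot be compared, then "antibody levels in post vaccination specimens will be compared with the geometric mean ALS antibody level against corresponding antigen in the same age group".

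The result feeds a secondary hypothesis that appears in two forms:

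- Secondary Hypotheses: "mucosal immune responses to at least two of the antigens in 50% or more participants in at least one of the dosing regimens". This form concerns the two youngest age groups and makes no mention of placebo.
- Data Analysis, Overview and general design: at least half of the fully immunized young children and infants must "show significantly higher mucosal immune responses to at least two out of the five vaccine antigens tested", by ALS and/or fecal assay, compared with placebo recipients.

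The Per Protocol Populations section requires a pre-vaccination measurement for stool and plasma, but not for ALS. Children without an ALS baseline therefore stay in the primary immunogenicity set.

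**The concern.** A fold rise over the child's own sample removes that child's usual level. Division by a group mean does not. A child whose level is naturally high can be scored as a responder although nothing changed, and how often this happens depends on the spread between children rather than on the vaccine.

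The sentence also leaves three things open: whether the mean is taken over pre-immune or other specimens, which arms contribute, and what multiple of the mean makes a response. Nor does it exclude scoring some children by one rule and others by another within a single rate.

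ALS IgA is the first-listed immunology endpoint and one of the two mucosal assays in the 50% hypothesis. On the absolute form of that hypothesis, an ineffective regimen could come close to the line or cross it.

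**Working it through.** The Protocol gives no false-responder rate for this rule, so there is no figure of its own to reproduce.

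**Inputs**

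- Threshold: 2-fold, log10(2) = 0.301 (Immunogenicity Analysis).
- Between-child log10 SD *s* of ALS levels: not given. Assumed 0.3 to 0.6. The upper value is borrowed from Sample Size Calculation, where 0.6 is the planning SD for CS6 from Swedish adults.
- Correlation *ρ* between a child's pre and post levels: not given, varied.
- Levels log-normal, and the reference mean taken as the centre of the unvaccinated distribution (assumptions).

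**1. Unvaccinated child, one antigen, one visit**

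Fallback at 2 × GM: P = 1 − Φ(0.301/*s*). Own baseline: P = 1 − Φ(0.301/(*s*·√(2(1 − *ρ*)))).

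| *s* | 2 × GM | Own, ρ = 0.5 | Own, ρ = 0.7 | Own, ρ = 0.9 |
|---|---|---|---|---|
| 0.3 | 1 − Φ(1.003) = 16% | 16% | 10% | 1% |
| 0.4 | 1 − Φ(0.753) = 23% | 23% | 17% | 5% |
| 0.6 | 1 − Φ(0.502) = 31% | 31% | 26% | 13% |

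If the cut is the GM itself, P = 50% at any SD. At 2 × GM the fallback has more false responders than the own-baseline rule only when *ρ* exceeds 0.5. For context, the Swedish adult trial (Table 3) reports 3% to 13% ALS responders per antigen on placebo.

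**2. At least two of five antigens, one visit**

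P = 1 − (1 − p)^5 − 5p(1 − p)^4, antigens independent:

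- p = 0.158: 18%
- p = 0.226: 32%
- p = 0.308: 49%

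At *s* = 0.6 with between-antigen correlation 0.3 to 0.5, simulation gives 45% to 42%. Counting a response after either dose, with correlation 0.8 over time and 0.3 between antigens, the range for *s* = 0.3 to 0.6 is 31–58% at 2 × GM, against 11–49% with own baselines. In the Swedish trial, 15% of placebo recipients (10% + 5%) responded to two or more antigens by ALS and/or fecal assay (Table 4).

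**3. Against the absolute 50% wording**

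Parts C and D plan nine vaccine regimens, four of 15 and five of 30. Suppose none works and every child is scored at 2 × GM at one visit. With a rate of 31.6%, P(≥8 of 15) = 0.066 and P(≥15 of 30) = 0.027, so the chance that some regimen reaches 50% is 1 − 0.934^4 × 0.973^5 ≈ 34%. At 18% it is about 1%. At 45% it is 98%.

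**4. When the vaccine works**

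With a common rise *f*, *s* = 0.6 and *ρ* = 0.8, the fold-rise SD is 0.6·√0.4 = 0.379.

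| *f* | 2 × GM: 1 − Φ((0.301 − log10 *f*)/0.6) | Own: 1 − Φ((0.301 − log10 *f*)/0.379) |
|---|---|---|
| 1 | 31% | 21% |
| 1.5 | 42% | 37% |
| 2 | 50% | 50% |
| 4 | 69% | 79% |

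So 2 × GM pulls the rate towards 50%: up below a 2-fold median rise, down above it. At a 4-fold rise the vaccine–placebo difference is 69 − 31 = 38 points, against about 57 with own baselines (78.6 − 21.4).

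**The case against.** A reader might infer that the fallback inflates a response rate that is formally tested against 50%. The documents do not support that.

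- **No test against 50%.** None is specified. Overview and general design refers the criterion to placebo, Immunogenicity Analysis makes vaccine versus placebo the main comparison, and the immunogenicity comparisons are called exploratory. If placebo children are scored the same way, both arms carry the false responders. This stands.
- **Inflation is not general.** At 2 × GM it needs a pre–post correlation above 0.5 and a median rise below 2-fold. Read as a fold-rise SD, as the Protocol uses it, 0.6 gives the same 31% false rate under the standard rule. This stands too. Only a cut at the plain mean inflates in every case tested.
- **The fallback is conditional and ALS-only.** Whole blood for ALS is scheduled at screening in every part. That the fallback will be used, or that baselines will be missing more often in the youngest, is not in the document. It is foreseeable all the same: the per-protocol set does not require an ALS baseline, and one 3.5 mL screening draw serves several assays.
- **Other readings.** The sentence could mean a uniform switch for a whole age group, and it does not itself mention responders or a threshold. But it follows the responder definition and is offered as the replacement for the pre–post comparison.
- **Earlier data.** Table 3, footnote c, reports comparable frequencies with and without participants lacking a day 0 specimen. The exception is fecal CS3 in one group, 12/24 overall against 10/16 with a day 0 specimen. These are adults and the substitution method is not stated, so this settles little for ALS in infants.

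A later analysis plan could supply the missing details. The choice of a group mean as comparator, however, is already fixed in the Protocol.

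**Conclusion.** The concern holds in limited form. The Protocol fixes a poor comparator and leaves its definition open. With no vaccine effect, 16–31% of children per antigen would count as responders at 2 × GM, or 50% at the GM, and 18–49% would respond to at least two of five independent antigens at one visit at 2 × GM.

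The rate is distorted rather than uniformly inflated. With pre–post correlation above 0.5 it is raised when the vaccine effect is small and, at 2 × GM, lowered once the median rise exceeds 2-fold. It should not be read against the absolute 50% wording. In the comparison with placebo the effect is dilution, not bias towards vaccine.

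The sizes rest on log-normal levels, an assumed SD of 0.3–0.6 and assumed correlations, none of which the Protocol gives for ALS in children. How many children would be scored this way is unknown.

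**What to change.** 1. Do not count children without their own ALS baseline in the 2-fold responder rate. Report the own-baseline rate separately, with its denominator.
2. Where baselines are insufficient in Parts C and D, make the comparison of post-vaccination log ALS levels with placebo at the same visit the main ALS analysis. Immunogenicity Analysis already plans comparisons of magnitude on the log scale.
3. If a fallback responder rate is still shown, derive one prespecified cut-off from the pre-immune/placebo distribution of that age group, apply it identically to every child including placebo recipients, and judge the 50% criterion only alongside the placebo rate.

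This is a wording change and needs no new samples. Reported response rates will be lower, and a high percentile costs sensitivity. For one antigen with a 4-fold rise, SD 0.6 and 30 versus 10 children, a 95th-percentile cut lies 1.645 × 0.6 = 0.987 above the centre. It gives 1 − Φ((0.987 − 0.602)/0.6) = 26% against 5%, and Fisher's exact test has about 14% power. At 2 × GM (69% against 31%) it has about 46%. Comparing log levels directly gives 0.602/(0.6·√(1/30 + 1/10)) = 2.75, or about 78% power by normal approximation (Φ(2.75 − 1.96)). That is why step 2 should carry the conclusion, and why the percentile in step 3 should be chosen with this loss in view.

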#### Sample Size Calculation:

Safety will be assessed by analyses of the following primary endpoints (events), where the unit of analysis in each case will be the proportion of participants with at least one event:

- Solicited gastrointestinal reactions
- Solicited systemic reactions
- Unsolicited Adverse events
- Adverse events where there is a reasonable possibility that the study product caused the event, i.e., are suspected adverse reactions
- Serious adverse events

The sample size for this study was selected to detect frequent adverse events. Given a planned sample size of groups of 15 adults, toddlers, and younger children each receiving one of varying dose levels of ETVAX with and without dmLT, the study will have an approximately 80% and 90% chance of observing at least one serious adverse event or adverse event of special interest for events that occur at a rate of 10.3% and 14.3%, respectively. Additionally, if no serious adverse events are observed in 15 participants, the upper bound of the one-sided 95% confidence interval on the rate of serious adverse event occurrence is approximately 18%.

For infant cohorts with 30 participants per dose group, the study will have an approximately 80% and 90% chance of observing at least one serious adverse event or adverse event of special interest for events that occur at a rate of 5.3% and 7.4%, respectively. If no serious adverse events are observed in 30 participants, the upper bound of the one-sided 95% confidence interval on the rate of serious adverse event occurrence is approximately 9.5%.

For infant cohorts, with 30 participants per group, this study is designed to provide approximately 73% power to detect as low as a 2-fold difference in geometric mean fold rise (post-vaccination / baseline) between comparisons of two groups

with varying doses of ETVAX and dmLT levels. This power calculation was based on the variability estimate, log10 standard deviation of 0.6, for CS6 obtained from a previous study of the vaccine in Sweden (VAC 003/OEV-121) and two-sample t-test using the 5% two-sided Type I error rate and 10% drop-out rate.

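### Friedman's test does not fit the independent groups it is listed for; separately, adjusting for baseline titre would add power to the magnitude comparisons without new samples

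*Protocol*

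**What the plan says.** The Protocol's Immunogenicity Analysis section introduces the main statistical comparison of response frequency and magnitude in vaccine and placebo recipients. It assigns "standard parametric and non-parametric methods whichever is applicable (i.e. Fisher's exact test, Chi-square test, t-test, and Mann-Whitney U test" to two groups, and the sentence continues "for two group comparisons; and Chi square test, generalized linear model, and Friedman's test". The items after the semicolon are not tied to any particular comparison. The section then says: "Statistical comparisons will be made between ETVAX dose levels and the dmLT levels, as well as comparison to the placebo group". GMT and GMFR are analysed on the log scale. No section names baseline titre as a covariate, and Kruskal-Wallis appears nowhere.

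Under Sample Size Calculation, the infant comparison is sized on a "2-fold difference in geometric mean fold rise (post-vaccination / baseline) between comparisons of two groups", with a "log10 standard deviation of 0.6, for CS6 obtained from a previous study of the vaccine in Sweden" and a "two-sample t-test using the 5% two-sided Type I error rate and 10% drop-out rate". The stated power is approximately 73%.

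On baseline samples, the Immunogenicity Analysis section plans a screening level for each participant, with a fallback to a group geometric mean where young children and infants yield too little pre-immune ALS specimen. The per-protocol populations require a pre-vaccination value for stool and plasma only. The full analysis population accepts pre- or post-vaccination data.

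**The concern.** There are two points of different weight.

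The first is an error in the text. Friedman's test ranks observations within blocks, such as one participant's successive samples. The groups to be compared here share no participants and are not matched. Friedman's test is nevertheless the only non-parametric test listed for magnitude in more than two groups. Followed literally, the analyst would have to invent blocks, and the result would depend on how they were formed.

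The second is efficiency. The two-group magnitude tests named, and the sizing, compare fold rise or post-vaccination level without the baseline as a covariate. Fold rise subtracts the whole log baseline and GMT ignores it. Regression on baseline uses it in the proportion that the data support. With infant power already low on the Protocol's own inputs, this gain is worth having, since stool and plasma baselines are already required for the per-protocol sets.

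**Working it through.** **Friedman's test against the design**

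- Part A has three separate groups of 15. Cohorts in Parts B and C are 15 vaccine and 10 placebo; in Part D they are 30 and 10.
- Friedman's test needs one observation per group in each block. Pairing 15 with 10 leaves 5 people unblocked, and 30 with 10 leaves 20. Where groups are equal (Part A, or vaccine groups across cohorts), blocks can be formed, but only by arbitrary pairing.
- Simulated consequence: four independent groups of 27, one shifted by log10(2), SD 0.6, 4,000 runs. Power was 43% for Kruskal-Wallis and 33% for Friedman's test with arbitrary blocks.
- In a single simulated data set (one group shifted by 0.25) re-paired 2,000 times, the Friedman p-value ran from 0.004 to 0.94. The Kruskal-Wallis p-value on the same data was 0.20.

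**The Protocol's own power figure**

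Inputs from Sample Size Calculation: 30 per group, 10% drop-out, hence 30 × 0.9 = 27; difference log10(2) = 0.301; SD 0.6; two-sided 5% t-test.

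- Non-centrality = 0.301 / (0.6 × √(2/27)) = 0.301 / 0.1633 = 1.843, with 52 degrees of freedom.
- Power = 44% (45% by normal approximation; 48% with all 30 per group). The stated 73% does not reproduce. A value near it (72.5%) appears if the factor 2 in the two-sample variance is left out.

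**Gain from baseline adjustment**

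Let ρ be the correlation of log baseline with log post-vaccination level, and s the common SD of both. The fold-rise variance is 2s²(1−ρ). The baseline-adjusted variance is s²(1−ρ²). Their ratio is (1+ρ)/2. The Protocol does not give ρ, so 0.2 to 0.8 is an assumed range.

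(a) If 0.6 is the SD of log fold rise, the adjusted SD is 0.6 × √((1+ρ)/2), with 51 degrees of freedom:

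| ρ | Adjusted SD | Non-centrality | Power, t-test on fold rise | Power, adjusted |
|---|---|---|---|---|
| 0.2 | 0.465 | 2.38 | 44% | 65% |
| 0.5 | 0.520 | 2.13 | 44% | 55% |
| 0.8 | 0.569 | 1.94 | 44% | 48% |

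(b) The text does not say whether 0.6 refers to fold rise or titre. If it is the SD of log titre, the fold-rise SD is 0.6 × √(2(1−ρ)) and the adjusted SD is 0.6 × √(1−ρ²):

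| ρ | Power, t-test on fold rise | Power, adjusted |
|---|---|---|
| 0.2 | 30% | 46% |
| 0.5 | 44% | 55% |
| 0.8 | 82% | 85% |

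On either reading the gain shrinks as ρ rises: 21, 11 and 4 points under (a), and 16, 11 and 4 under (b).

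**The case against.** On Friedman's test, the best defence is that the items after the semicolon have no stated purpose. The same section plans comparisons of pre- and post-vaccination levels, and Appendix I schedules repeated stool, plasma and ALS samples, where the test could fit. This shows a legitimate use, but not that the Protocol assigns it: the sentence concerns vaccine and placebo recipients, and the list opens with i.e. A reader might infer that any resulting p-value would be invalid. That goes too far. With blocks fixed in advance and without regard to the data, the test would keep its null level; the harm is arbitrariness and lost power.

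On baseline, the objections largely stand and set the limits of the point:

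- A reader might infer that the Protocol fixes unadjusted t-tests. It does not. It says whichever method is applicable, the listed generalized linear model could carry a baseline covariate, and a detailed SAP (not shown here) is announced. Silence on covariates is no error.
- A reader might infer that every participant has a baseline titre. The ALS fallback and the two population definitions contradict this.
- A reader might infer that chance baseline imbalance biases the results. In a randomised vaccine-placebo comparison it adds variance, not bias. Dose and dmLT groups are recruited in successive cohorts, so that reassurance does not extend to them automatically, but nothing in the Protocol shows that baselines differ between cohorts.
- The endpoints are secondary, and the Protocol calls all immunogenicity comparisons exploratory.

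**Conclusion.** The Friedman point holds as an error in the named methods. The test does not match the between-group comparisons that its sentence describes, and no suitable non-parametric alternative for more than two independent groups is given. It is easily corrected, and it bears on exploratory immunogenicity analyses, not on the primary safety endpoints.

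The baseline point holds as a recommendation only. Its size depends on a correlation that the Protocol does not give, on equal pre and post variances, and on which SD 0.6 denotes. Over ρ from 0.2 to 0.8 the gain is about 4 to 21 percentage points at 27 per group. It would be wrong to infer that adjustment rescues the stated 73%. If 0.6 is the SD of log fold rise, adjusted power stays between 48% and 65%. If 0.6 is the SD of log titre, power passes 73% at ρ = 0.8, but there the unadjusted fold-rise test already does so. The gap between 73% and 44% is a separate fault in the sample size paragraph.

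**What to change.** 1. In Immunogenicity Analysis, replace Friedman's test by Kruskal-Wallis for comparing more than two independent groups. If Friedman's test was meant for a participant's successive samples, say so and confine it to that use.
2. State the main magnitude comparison, per antigen, as a linear model of log10 post-vaccination level on treatment group and log10 baseline level, for stool and plasma. Apply it to ALS where a baseline exists, and keep the Protocol's existing fallback otherwise. Report adjusted GMT ratios with 95% confidence intervals, and keep unadjusted GMT and GMFR as description.

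Both are changes of wording in the Protocol or the SAP, to be made before database lock and unblinding of each age group. Neither needs extra samples, visits or participants. The one analytic cost is a degree of freedom for the baseline term.
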